- at least 3 of the first 8 participants to be included in the Cohort 2 RAL-unexposed group interim analysis have had treatment discontinuation due to non-life threatening Grade 3 or 4 severity SADR, judged to be at least possibly treatment related;

OR

- if after the Cohort 2 RAL-unexposed group interim analysis,
 - there was no dose adjustment and at least 6 of 20 participants to be included in Cohort 2 final analysis have had treatment discontinuation due to non-life threatening Grade 3 or 4 severity SADR, judged to be at least possibly treatment related; or
 - there was a dose adjustment and at least 4 of the 12 participants on the final dose for Cohort 2 have had treatment discontinuation due to non-life threatening Grade 3 or 4 severity SADR, judged to be at least possibly treatment related.

Following any temporary suspension of accrual, the team will further review the safety data within 48 hours of notification of the event to determine if continuation of accrual is appropriate. If the team, including the study chair, the DAIDS medical officer of record and Merck representatives, agrees that the study drug is likely to be safe for additional participants, they may decide to allow accrual to resume. However, the P1110 SMC will be informed of this decision, and the study will not reopen without the approval of this committee. The SMC may ask for any data it may want to review before making its decision. Regulatory agencies will be notified of the event and the team's and SMC's decision.

8.521 Final Evaluation of Cohort 1 Safety Data

At final evaluation of the Cohort 1 RAL-exposed or RAL-naïve groups, safety guidelines will be assessed on infants on the final dose for each group in Cohort 1 using safety data through week 6 of life. If none of the participants has experienced a new life-threatening event or death judged to be an SADR or a new Grade 4 event that is probably or definitely attributable to the study medication; and no more than 25% of the participants have had treatment discontinuation due to non-life threatening Grade 3 or 4 severity SADR at least possibly related to the study drug, then final dose in Cohort 1 has passed the safety guidelines. Otherwise the team will review the

safety data and will consult with the P1110 SMC to determine whether it is safe to proceed to Cohort 2 and under what conditions this will be allowed to occur.

8.522 Interim Evaluation of Cohort 2 RAL-naïve Group Safety Data

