8.53 Probabilities of Failing the Safety Guidelines

The safety guidelines will be assessed at final analysis of Cohort 1, at interim analysis of Cohort 2 and at final analysis of Cohort 2, based on safety data through 6 weeks of life on samples of 12, 8, and maximum of 20 infants, respectively. Given these small sample sizes, the information available for safety decisions will be imperfect. Two types of sampling errors are possible:

- 1) In a group where the true rate of toxicity is too high to warrant increased exposure to the current starting dose of the medication, the sample data may pass the safety guidelines;

- 2) In a group where the true rate of toxicity is low enough that further exposure to the current starting dose is warranted, the sample data may fail the guidelines.

The extent to which the safety guidelines protect against the errors described above can be assessed by examining various hypothetical rates of "true toxicity" which could occur, if the study medication were used extensively among the participant population at the dose level under question. The hypothetical situations presented in Tables 11,12, and 13 are for the sample sizes of the 12 participants in Cohort 1, the first 8 participants for the interim analysis for Cohort 2, and 20 participants for final analysis of Cohort 2, respectively. Should there be a dose change following the interim analysis of Cohort 2, then only the 12 remaining participants will be exposed to the new dose; in that case the probabilities presented in Table 11 will apply. Tables 11,12 and 13 show the probabilities of failing the safety guidelines for a range of conditions under which a given dose level would cause a high incidence of severe and life threatening SADR's to conditions under which severe SADR's would be relatively rare and would not be life threatening. For each of these hypothetical situations, we assume that the sample is drawn from the participant population and that the safety guidelines for Cohort 1 (Section 8.521), interim analysis for Cohort 2 (8.522) and final analysis for Cohort 2 (Section 8.523) are followed.

Table 11.
Probability of Failing Safety Guidelines for a Sample of 12 Participants for Final
Analysis of Cohort 1 Under Potential Rates of True Toxicity

True Toxicity Rates		Probability of Failing Safety Guidelines

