Non-life threatening SADR that would result in treatment discontinuation, excluding Grade 4 events probably or definitely attributable to study medication	Death or life- threatening SADR or Grade 4 events probably or definitely attributable to study medication	
0.50	0.00	0.93
0.50	0.05	0.97
0.50	0.25	1.00
0.25	0.00	0.35
0.25	0.05	0.67
0.25	0.25	0.99
0.05	0.00	0.00
0.05	0.05	0.46
0.05	0.25	0.97
0.00	0.05	0.46
0.00	0.25	0.97

Table 12.
Probability of Failing Safety Guidelines for a Sample of 8 Participants for Interim
Analysis of Cohort 2 under Potential Rates of True Toxicity

True Toxicity Rates		
Non-life threatening SADR that would result in treatment discontinuation, excluding Grade 4 events probably or definitely attributable to study medication	Death or life-threatening SADR or Grade 4 events probably or definitely attributable to study medication	Probability of Failing Safety Guidelines
0.50	0.00	0.86
0.50	0.05	0.93
0.50	0.25	1.00
0.25	0.00	0.32
0.25	0.05	0.57
0.25	0.25	0.95
0.05	0.00	0.01
0.05	0.05	0.34
0.05	0.25	0.90
0.00	0.05	0.34
0.00	0.25	0.90

Table 13.
Probability of Failing Safety Guidelines for a Sample of 20 Participants for Final Analysis of Cohort 2 Under Potential Rates of True Toxicity

True Toxicity Rates		
Non-life threatening SADR that would result in treatment discontinuation, excluding Grade 4 events probably or definitely attributable to study medication	Death or life-threatening SADR or Grade 4 events probably or definitely attributable to study medication	Probability of Failing Safety Guidelines
0.50	0.00	0.98
0.50	0.05	1.00
0.50	0.25	1.00
0.25	0.00	0.38
0.25	0.05	0.80
0.25	0.25	1.00
0.05	0.00	0.00
0.05	0.05	0.64
0.05	0.25	1.00
0.00	0.05	0.64
0.00	0.25	1.00

For example, Table 11 shows that for a sample of size 12, there is a 97% chance of failing the safety guidelines under conditions in which the true rate of life-threatening toxicity is 5% and the rate of non-life threatening SADR is 50%. Assuming that it would be undesirable to accrue additional participants at a dose that had these true rates of adverse events, the 3% chance of NOT failing the safety guidelines would represent the probability of error.

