This is a Phase I multi-center, open label, non-comparative study to evaluate the safety and pharmacokinetics (PK) of raltegravir (RAL) administered to HIV-1-exposed full-term (≥ 37 weeks of gestation) neonates at high risk of acquiring HIV-1 infection. The goal is to determine the appropriate dosing regimen of RAL oral granules for suspension that can be safely administered to neonates and infants in the first 6 weeks of life.

This study will enroll approximately 50 neonates in order to accrue a minimum of 32 PK evaluable high risk HIV-1-exposed neonates and their mothers across Cohort 1 and Cohort 2. Mother-infant (M-I) pairs will enroll at the time of delivery up to 48 hours of life, which is the latest time for administration of first neonatal RAL dose. Cohort 1 opened first and accrual to Cohort 2 was contingent upon neonates enrolled in Cohort 1 successfully meeting safety criteria and providing adequate PK data so that the dosing regimen was developed for daily dosing through 6 weeks of age for Cohort 2. Through Protocol Version 1.0 LoA #2 Cohort 2 RAL-naïve group was opened to accrual with the following dosage: 1.5 mg/kg once daily during Days 1-7 of life, 3.0 mg/kg twice daily during Days 8-28 of life, and 6.0 mg/kg twice daily during Days 29-42 of life.

At the time of this SAP update, Cohort 1 (both RAL-naïve and RAL-exposed groups) is closed to accrual and follow-up and Cohort 2 RAL-naïve group is closed to accrual but follow-up is ongoing. The final accrual numbers are 10 M-I pairs for Cohort 1 RAL-naïve, 6 M-I pairs for Cohort 1 RAL-exposed, and 26 M-I pairs for Cohort 2 RAL-naïve groups under protocol Version 1.0. The team estimated that the study will take 3 years to fully accrue under protocol

Version 1.0. Protocol Version 2.0 is currently being drafted and if approved, will open accrual to Cohort 2 RAL exposed group.

PK evaluable infants are those whose PK results provide data on the primary PK parameters of interest. If a participant has unevaluable PK data, which reflects uncertainty about appropriate exposure to the study medication, the participant will be excluded from PK analyses and will be replaced. PK analyses will be done by the protocol pharmacologist.

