4.7 Safety Analysis for Dose Finding and Possible Early Study Discontinuation

Purpose:

To list the endpoints and summary tables of safety analysis for dose finding and possible early study discontinuation. Reports will be generated at full accrual to cohort 1 and at interim and full accrual to cohort 2.

Analysis Program Validation:

Code review required. Primary analysis will require double coding.

Data:

Infant Safety Data are adverse clinical and laboratory events reported in Hematology and Liver Chemistries ((LBW0093), Signs/Symptoms (PE6831), Diagnosis (PE6852) and Death (PE1414) CRFs. (The following variables in the SDAC SAS datasets will be used: EVENTDSC, EVNGRDE, FORMNM and FORMTYP in EVENTS table; TRACKCD and RELATSP in TRAC table; and RAL1ST, RAL1RS, RAL2ST, RAL2RS in TXW0276 CRF).

Analysis:

Infants who have been excluded from the PK analyses, due to evidence of problematic exposure to the study medication, will be excluded from evaluation of the safety guidelines. AEs and SADRs will exclude events classified by the team as “baseline” or “ongoing baseline” events.

- a) Safety endpoints for Cohorts 1 and 2 in dose finding and possible early study discontinuation
 - Safety endpoints
 - based on data through 6 weeks (i.e. through 49 days) of life:
 - i. Life threatening event or death judged to be a SADR or Grade 4 event that is judged to be probably or definitely attributable to the study medication
 - ii. Treatment discontinuation due to non-life threatening Grade 3 or 4 severity SADR, judged to be at least possibly treatment related

Notes: During the regular monitoring, the team will assess whether an AE is life threatening and the assessment will be entered in the TRAC table. Treatment discontinuation due to an AE will be on the TXW0276 CRF.

- b) Summary table for the interim and cohort full accrual safety reports (analysis for dose finding and possible early study discontinuation).
Note: Only the overall summary will be provided since we are expecting very few infants meeting the safety endpoint.

Table: Summary table showing number (%) of the proportion of infants who meet the safety endpoints for dose finding and possible early study discontinuation.

Table 7: Summary of Infants Meeting the Safety Endpoints for Dose Finding and Possible Early Study Discontinuation

Endpoint	Number and Proportion

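### Table 11 gives the Cohort 1 safety rule's failure probabilities for 12 infants, but Section 8.521 applies the rule per exposure group to about 4 and 6, and SAP Table 7 cannot show a per-group result

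*Protocol*

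**What the plan says.** **The rule.** Protocol Section 8.521 states that "safety guidelines will be assessed on infants on the final dose for each group in Cohort 1 using safety data through week 6 of life". A group passes only if two conditions are met. The first begins "If none of the participants has experienced a new life-threatening event or death judged to be an SADR" and also bars Grade 4 events probably or definitely attributed to study drug. The second is that "no more than 25% of the participants have had treatment discontinuation due to non-life threatening Grade 3 or 4 severity SADR", counting SADRs judged at least possibly drug-related. Section 6.21 then opens Cohort 2 separately for the matching exposure group.

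**The stated operating characteristics.** Section 8.53 gives the sample sizes as "samples of 12, 8, and maximum of 20 infants, respectively", says that the Section 8.521 rule is followed, and computes Table 11 for 12 infants. Its worked example, at 50% non-life-threatening and 5% life-threatening toxicity, says "there is a 97% chance of failing the safety guidelines" and treats the remaining 3% as the probability of error. The section also assigns Table 11 to the 12 Cohort 2 infants who would follow a dose change.

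**The numbers enrolled.** SAP Section 2 reports: "The final accrual numbers are 10 M-I pairs for Cohort 1" RAL-naïve, and 6 for Cohort 1 RAL-exposed. Protocol Section 1.29 agrees. It adds that the first 6 RAL-naïve infants had a 3 mg/kg first dose and later ones 2 mg/kg, and that 15 of the 16 infants had evaluable PK.

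**The reporting.** For the dose-finding endpoints (Table 7), SAP Section 4.7 says: "Only the overall summary will be provided since we are expecting very few infants meeting the safety endpoint".

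**The concern.** The rule and the table that describes it use different denominators. With so few infants, the denominator largely determines how often an unsafe dose is caught, especially for a criterion that tolerates no life-threatening events. Section 8.53 is the protocol's only quantitative account of the error risk at this evaluation, and a reader would take its 3% as the chance of wrongly passing a Cohort 1 group.

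The SAP table has a related weakness. A percentage limit applied within a group cannot be checked from a single count across groups. The reporting gap also reaches beyond Cohort 1, because Section 8.523 applies its final evaluation to each Cohort 2 group and Version 2.0 opens the RAL-exposed one.

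**Working it through.** **Inputs**
- RAL-naïve infants on the final dose: 10 − 6 = 4 (SAP Section 2; Protocol Section 1.29).
- RAL-exposed infants: 6, all on one regimen (same sources; SAP Section 4 lists the subgroups).
- Life-threatening criterion: none allowed.
- Discontinuations allowed: c = floor(0.25n), which is 3 of 12, 1 of 4 and 1 of 6.

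**Formula.** Let p1 be the non-life-threatening discontinuation rate and p2 the life-threatening rate, as mutually exclusive outcomes. Then

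P(fail) = 1 − Σ (k = 0 to c) C(n,k) · p1^k · (1 − p1 − p2)^(n−k)

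**Reproducing the plan's figure.** For n = 12, c = 3, p1 = 0.50, p2 = 0.05, the four terms are 0.0001 + 0.0009 + 0.0056 + 0.0208 = 0.0274. P(fail) is therefore 0.973, stated as 0.97. The formula matches every row of Tables 11, 12 and 13 to two decimals.

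**The same example at the group sizes**
- n = 4: 0.45^4 + 4(0.50)(0.45^3) = 0.0410 + 0.1823 = 0.2233, so P(fail) = 0.78.
- n = 6: 0.45^6 + 6(0.50)(0.45^5) = 0.0083 + 0.0554 = 0.0637, so P(fail) = 0.94.

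The chance of wrongly passing is thus 22% or 6%, against the stated 3%.

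**Life-threatening events alone.** Here P(fail) = 1 − (1 − p2)^n. At 5%: 1 − 0.95^4 = 0.19 and 1 − 0.95^6 = 0.26, against 1 − 0.95^12 = 0.46. At 25%: 0.68 and 0.82, against 0.97.

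| p1 / p2 | Table 11 (n=12) | n=4 | n=6 |
|---|---|---|---|
| 0.50 / 0.00 | 0.93 | 0.69 | 0.89 |
| 0.50 / 0.05 | 0.97 | 0.78 | 0.94 |
| 0.25 / 0.00 | 0.35 | 0.26 | 0.47 |
| 0.25 / 0.05 | 0.67 | 0.42 | 0.63 |
| 0.25 / 0.25 | 0.99 | 0.81 | 0.94 |
| 0.05 / 0.00 | 0.00 | 0.01 | 0.03 |
| 0.05 / 0.05 | 0.46 | 0.20 | 0.29 |
| 0.05 / 0.25 | 0.97 | 0.69 | 0.83 |
| 0.00 / 0.05 | 0.46 | 0.19 | 0.26 |
| 0.00 / 0.25 | 0.97 | 0.68 | 0.82 |

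**Sensitivity to one exclusion.** Section 8.5 drops infants excluded from PK for problematic exposure. The documents give neither the group of the infant without evaluable PK nor the reason. If that infant is dropped, one group becomes 3 (no discontinuation allowed) or 5 (one allowed). The worked example is then 0.91 or 0.88, and the 5% life-threatening row 0.14 or 0.23.

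**Pooled reading.** If final-dose infants from both groups were combined, n would be 4 + 6 = 10, again not 12. With 2 discontinuations allowed, the worked example is 0.98 and the 5% life-threatening row 0.40.

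**SAP Table 7.** Two discontinuations among 4 RAL-naïve final-dose infants is 50%, and two among 6 RAL-exposed is 33%; either fails Section 8.521. As an overall count the same two are 2/16 = 12.5%, or 2/10 = 20% if only final-dose infants are counted. Both sit below the 25% limit.

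**The case against.** **Table 11 is not miscalculated.** A reader might infer an arithmetic error or a false worked example. The documents do not support that: the table title and the example both specify 12 infants, every row reproduces, and n = 12 remains right for the Cohort 2 dose-change path. The fault is only that the table is offered as a description of Section 8.521.

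**Protection is not lower everywhere.** At 25%/0 the n=6 group fails more often than stated (0.47 against 0.35), and at 5%/0 both groups fail slightly more often. For n=6 the worked example shifts only from 0.97 to 0.94; the large shift is at n=4.

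**Other safeguards exist.** Section 8.52 suspends accrual cohort-wide after any life-threatening SADR. Under an assumed common 5% rate that fires with probability 1 − 0.95^16 = 0.56 over 16 infants. Section 6.2 also required several parties to approve the Cohort 2 dose. These are real protections, but they lie outside Table 11 and do not make it describe the per-group evaluation. Nor does combining the groups: under common rates the chance that at least one fails is 0.99 for the worked example, but only 0.40 for a 5% life-threatening rate, and the first doses and gates differ by group.

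**No Cohort 1 decision is open.** This stands. The Cohort 2 RAL-exposed group has a minimum of 8 infants, where the 25% limit allows 2 discontinuations, so Table 12 already gives the right figures at that size. A reader might also infer that Cohort 1 was wrongly passed, or that the final report will cite the pass as support for the dose. Neither is in the documents: no Cohort 1 event counts against the rule are given, and SAP Section 4.6 builds the final report on proportions with exact 90% intervals, shown by dose subgroup in SAP Table 6.

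**The SAP predates Version 2.0.** SAP Version 3.0 limits the Cohort 2 guideline assessments to the RAL-naïve group, so an overall count there is one group. That explains Table 7, but it leaves the per-group Cohort 1 rule and the later RAL-exposed evaluation without a matching table.

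**Conclusion.** The mismatch is real. Section 8.53 attributes to the Section 8.521 rule operating characteristics that belong to a sample of 12, while the rule works on about 4 and 6 infants. The understatement of error is substantial for the RAL-naïve group and for life-threatening events in both groups. It is small for the RAL-exposed group in the worked example, and reversed in a few entries.

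This rests on three assumptions: that Section 8.521 is applied group by group, as its wording and the group-specific opening in Section 6.21 indicate; that the final RAL-naïve regimen is the one given after the first 6 infants; and that no infant is excluded, with sizes of 3 or 5 covered above. The group sizes are realised counts, not planned ones. The conclusion concerns the accuracy of the stated assurance and the ability to report against the rule. It does not show that any dose was unsafe or that opening Cohort 2 was wrong.

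**What to change.** 1. In Section 8.53, add failure probabilities for n=4 and n=6 as the Cohort 1 per-group evaluation, with a note on 3 or 5 if an infant is excluded. Keep the n=12 table and example, and label them as applying to the Cohort 2 dose-change path.
2. If a pooled Cohort 1 evaluation was intended, reconcile 8.521 with 8.53 and state the pooled denominator.
3. State beside the table that the Section 8.52 suspension rule is additional, cohort-wide protection that the table does not include.
4. Produce SAP Table 7 by exposure group, restricted to infants on the final dose, so that the limits in 8.521 and 8.523 can be assessed, including for the Cohort 2 RAL-exposed group.

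The cost is one recalculation and some added table columns. No infants, visits or decision rules change. Most of the stated Cohort 1 protection will look weaker once restated.

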8.6 Accrual Rate Evaluation

Accrual to this study will be monitored by the IMPAACT leadership in accordance with standard operating procedures. The team monitored site registration and accrual to Cohort 1 RAL-naïve, Cohort 1 RAL-exposed groups, and Cohort 2 RAL-naïve group as specified in protocol Version 1.0. For Cohort 2 RAL-exposed group, if less than 4 infants have been accrued after 8 months of this study group opening, the team will re-assess the reasons for low accrual, and will possibly amend or close the protocol accordingly.

8.7 Analyses

8.7.1 Primary and Secondary Safety Analyses of the Primary Safety Endpoints

To evaluate the safety and tolerability of RAL through 6 weeks of life, descriptive statistics will be calculated summarizing the safety data from study entry through 6 weeks of life from all safety evaluable infants in the four study groups: (i) Cohort 1 RAL-naïve, (ii) Cohort 1 RAL-exposed, (iii) Cohort 2 RAL-naïve, and (iv) Cohort 2 RAL-exposed infants. Overall summary statistics for the cohort will be provided if the data suggests that there is no difference between RAL-naïve and RAL-exposed infants within that cohort. The primary safety analysis will be the calculation of the point and 2-sided 90% confidence interval (CI) using the Clopper-Pearson exact method estimates of the proportion of infants meeting the primary toxicity endpoint of adverse event Grade 3 or 4 severity or death. Secondary safety analyses will include point and 90% CI estimates of infants with a SADR of Grade 3 or 4 severity or death. Table 14 shows the precision with which confidence intervals around proportions of serious adverse events can be estimated, for the 12 participants in Cohort 1 and for the 8 and 20 participants in the interim and final analyses for Cohort 2.

Table 14
90% Confidence Intervals Around Potential Proportions
of Infants Meeting a toxicity Endpoint^a

Number of participants	Proportion of participants meeting toxicity endpoint	Clopper-Pearson 90% CI
8	0.00	(0.00, 0.37)
	0.25	(0.03, 0.65)
	0.50	(0.16, 0.84)
12	0.00	(0.00, 0.26)
	0.25	(0.05, 0.57)
	0.50	(0.21, 0.79)
20	0.00	(0.00, 0.17)
	0.10	(0.01, 0.32)
	0.20	(0.06, 0.44)
	0.50	(0.27, 0.73)

^a Clopper-Pearson exact confidence interval estimates using SAS Version 9.2.

The primary safety analyses population will include all infants who have had at least one dose of raltegravir. For Cohort 2 RAL-naïve group, if there was dose adjustment after the interim analysis, a sensitivity analysis will be performed on infants who were enrolled after dose adjustment and only took the adjusted dose. Patients who had an idiosyncratic dose adjustment, based on extreme PK data, will be included in the primary analysis.

However, this adjustment will be acknowledged in the narrative part of the report where these results are described.

8.711 Secondary Analyses

To assess the safety and tolerability of RAL through 24 weeks of life, descriptive statistics will be calculated summarizing the proportion of infants who had an adverse event of Grade 3 or 4 severity or death based on safety data from study entry through 24 weeks of age on all safety evaluable infants in each of the four study groups. A similar analysis will be done to summarize proportion of infants who had an SADR of Grade 3 or 4 severity or death.

To investigate the relationship between neonatal raltegravir elimination and UGT1A-1 genotype, participants will be divided into subgroups, based on whether or not they exhibit polymorphisms on UGT1A-1. Descriptive analyses will be performed to compare these subgroups with respect to measures of central tendency and dispersion for raltegravir AUC.

Similar descriptive analyses will also be performed to investigate the association of UGT1A1 (*28/*28) and SLCO1B3 (rs2117032-C/T) with hyperbilirubinemia. If the sample size and the data distributions make this possible, a logistic regression model predicting for probability of neonatal hyperbilirubinemia with UGT1A1 (*28/*28) genotype, SLCO1B3 (rs2117032-C/T) genotype, gestational age and gender as predictors will be fitted on the pooled data across the two cohorts. Note that the sample size may be too small and/or there may be insufficient cases of hyperbilirubinemia to make this possible. If this analysis can be done, it will have minimal power, but the size and directionality of effects will be compared with those predicted on the basis of previous findings.

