- interim and full cohort accrual safety reports: at full accrual to Cohort 1, at interim analysis when 8 participants have been accrued to Cohort 2 (safety analysis only) and at full accrual to Cohort 2 RAL-naïve group; and
- SDAC final reports: the first report will focus on Cohort 1 (both RAL naïve and exposed groups) and Cohort 2 RAL naïve group. Should protocol Version 2.0 be approved and Cohort 2 RAL-exposed group be opened to accrual, a second report will be generated at study closure to follow-up for Cohort 2 (both RAL naïve and exposed groups).

When applicable, separate summary tables will be generated for the women and their infants. Separate summary tables will be generated for each cohort since Cohort 1 neonates will receive two single RAL dosing while Cohort 2 neonates will receive daily RAL dosing through 6 weeks of life. Summary statistics for subgroups of infants will be provided alongside the overall cohort summary statistics. Infant subgroups will be defined in terms of infant in utero RAL exposure and RAL dosing. For Cohort 1, there are 3 infant subgroups: (i) RAL-naïve (3mg/kg-3mg/kg), (ii) RAL-naïve (2mg/kg-3mg/kg), and (iii) RAL-exposed (1.5mg/kg-3mg/kg). Cohort 2 RAL-naïve group only has one dosing which was specified in **Section 2**.

The interim and full cohort accrual safety reports will be prepared for the core team and, if necessary, for the SMC. These reports will include information concerning Screening and Entry, Participant and Study Status, Baseline, and Safety summary tables. Unless otherwise noted the SDAC final reports will contain all summary tables.

Additional participant listings necessary in writing up the SDAC final report will be generated and will be used internally at SDAC. Highlights of these listings will be included in the SDAC final report. These participant listings will be provided to the manuscript writing team. The manuscript writing team, which is a subset of the protocol team, will be identified by the protocol team.

The analysis of the PK data will be performed by the protocol pharmacologists and thus, not included in this document.

Validation requirements as per SDAC SOPs will be as follows:

- a. All dataset creation programs will be validated with double coding for the primary and secondary safety endpoints.
- b. All study-specific formats will be validated.
- c. Validation of analysis programs is specified in the following subsections.

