secondary safety endpoints for final analysis)

Note: Summary tables will include statistics for infant subgroups and overall and listing will include information on infant in utero RAL exposure and RAL dosing.

Table: Summary tables showing number (%) and the 2-sided 90% confidence interval (CI) using the Clopper-Pearson exact method estimates of the proportion of infants meeting the primary and secondary safety endpoints(will provide as footnote number of infants with missing data). The primary analysis will be on the primary safety endpoint.

Table 6: Proportion of Infants Meeting the Primary Safety Endpoint (mock-up table)

RAL-naïve			RAL-exposed	Overall
3mg/kg-3mg/kg	2mg/kg- 3mg/kg	Overall	1.5mg/kg-3mg/kg	
N (%) [90% CI]	N (%) [90% CI]	N (%) [90% CI]	N (%) [90% CI]	N (%) [90% CI]

Note: Similar table will be generated for Cohort 2 with appropriate column labels appropriate for Cohort 2 subgroups of infants.

Table: Summary tables of worst adverse events (laboratory, signs/symptoms and diagnoses) for each of the primary and secondary safety endpoint.

Table: Summary of worst grade baseline events (laboratory, signs/symptoms and diagnoses).

Table: Listing of reasons for infant death and age (weeks) at death.

Table: Summary table showing number (%) and the 2-sided 90% confidence interval (CI) using the Clopper-Pearson exact method estimates of the proportion of infants who had total bilirubin exceeding 16.0 mg/dL, or received phototherapy, transfusion therapy or other therapies for hyperbilirubinemia.

The following SDAC internal listings will be generated to facilitate the write-up of the SDAC final report. The listings will also be provided to the manuscript writing team. SDAC public IDs will be used and no identifying dates will be provided.

- a. Per infant listings of baseline events, AEs and SADRs with site and team assessment of drug attribution.
- b. Per infant listing of ARVs from TXW0276 and PE0421.

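### Table 14 gives the precision of the primary safety estimate at 12 and 20 infants, which are not the sizes of the safety groups: it is too favourable for Cohort 1 RAL-exposed and too pessimistic for Cohort 2 RAL-naïve

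*Protocol*

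**What the plan says.** **The estimate.** Protocol Section 8.7.1 makes the primary safety analysis the "point and 2-sided 90% confidence interval (CI) using the Clopper-Pearson exact" estimate of the proportion of infants with a Grade 3 or 4 adverse event or death through 6 weeks of life. SAP Section 4.6 agrees on level and method: "the 2-sided 90% confidence interval (CI) using the Clopper-Pearson exact method estimates of the proportion of infants meeting the primary and secondary safety endpoints".

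**The analysis set.** The data are summarised "from all safety evaluable infants in the four study groups": Cohort 1 RAL-naïve, Cohort 1 RAL-exposed, Cohort 2 RAL-naïve and Cohort 2 RAL-exposed. On the population, Section 8.7.1 states: "The primary safety analyses population will include all infants who have had at least one dose of raltegravir".

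**Cohort totals.** The protocol makes these conditional: "Overall summary statistics for the cohort will be provided if the data suggests that there is no difference between RAL-naïve and RAL-exposed infants". The SAP, in the opening of Section 4, always gives them: "Summary statistics for subgroups of infants will be provided alongside the overall cohort summary statistics".

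**The precision.** Table 14, headed as 90% intervals, is offered "for the 12 participants in Cohort 1 and for the 8 and 20 participants in the interim and final analyses for Cohort 2". Protocol Section 8.4 says that the 12 and 20 are PK-evaluable minimums chosen for the PK analysis.

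**The group sizes.** SAP Section 2 gives final accrual as 10 mother-infant pairs for Cohort 1 RAL-naïve, then "6 M-I pairs for Cohort 1 RAL-exposed, and 26 M-I pairs for Cohort 2" RAL-naïve. Protocol Section 1.29 also reports the 10 and 6. The Schema asks for at least 8 PK-evaluable infants in Cohort 2 RAL-exposed.

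**The concern.** Table 14 is the plan's only statement of how precisely the primary safety proportion will be estimated. Its sizes are PK-evaluable cohort minimums, whereas the estimates are made per exposure group on everyone dosed. A reader who applies the n=12 row to the Cohort 1 RAL-exposed infants will think that zero events excludes rates that six infants cannot exclude. A reader who applies the n=20 row to Cohort 2 RAL-naïve, the main multiple-dose group, will underrate what it can show.

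The sizes were available. The SAP that lists 10, 6 and 26 is dated 3 January 2017, protocol Version 2.0 is dated 18 January 2017, and Section 8.4 of that version says these three groups were fully accrued.

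**Working it through.** **Inputs**
- Level and method: 2-sided 90%, Clopper-Pearson (protocol Section 8.7.1; SAP Section 4.6).
- Enrolled: 10, 6 and 26 (SAP Section 2). Cohort 2 RAL-exposed: at least 8 (protocol Schema and Section 8.4).
- Pooled: 10 + 6 = 16 in Cohort 1; 26 + 8 = 34 in Cohort 2, a minimum because the 8 is a minimum.
- Assumption: every enrolled infant received at least one dose.

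**Formula.** For x events in n infants and a = 1 − confidence level, the lower limit is the a/2 quantile of Beta(x, n−x+1) and the upper limit is the 1−a/2 quantile of Beta(x+1, n−x). With x = 0 the upper limit is 1 − (a/2)^(1/n).

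**Step 1: reproduce Table 14.** None of its 10 rows reproduces at 90%; all 10 reproduce to two decimals at 95%. The zero-event rows:

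| n | Printed upper limit | 95%: 1 − 0.025^(1/n) | 90%: 1 − 0.05^(1/n) |
|---|---|---|---|
| 8 | 0.37 | 0.369 | 0.312 |
| 12 | 0.26 | 0.265 | 0.221 |
| 20 | 0.17 | 0.168 | 0.139 |

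The size question therefore has to be measured both against what is printed and against the same row at a true 90%.

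**Step 2: zero-event upper limits at the sizes analysed (90%)**

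| Estimate | n | Upper limit | Table 14 row | Printed | Row at true 90% |
|---|---|---|---|---|---|
| Cohort 1 RAL-exposed | 6 | 0.39 | 12 | 0.26 | 0.22 |
| Cohort 1 RAL-naïve | 10 | 0.26 | 12 | 0.26 | 0.22 |
| Cohort 1 pooled | 16 | 0.17 | 12 | 0.26 | 0.22 |
| Cohort 2 RAL-naïve | 26 | 0.11 | 20 | 0.17 | 0.14 |
| Cohort 2 RAL-exposed | 8 (minimum) | 0.31 | 8 (labelled interim) | 0.37 | 0.31 |
| Cohort 2 pooled | 34 (minimum) | 0.08 | 20 | 0.17 | 0.14 |

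**Step 3: separate size from level**
- Cohort 1 RAL-exposed: 0.39 − 0.26 = 0.13 against the printed row; 0.39 − 0.22 = 0.17 like for like at 90%. The wrong level hides part of the shortfall.
- Cohort 2 RAL-naïve: 0.17 to 0.14 comes from the level and 0.14 to 0.11 from the size, about half each.
- Cohort 1 RAL-naïve: 0/10 at 90% agrees with the printed n=12 figure only because that figure is a 95% limit.

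**Step 4: a 50% event rate.** 3/6 gives 0.15 to 0.85, a width of 0.69. The n=12 row prints 0.21 to 0.79 (width 0.58); at a true 90% it is 0.25 to 0.75 (width 0.51). 13/26 gives 0.33 to 0.67; the n=20 row prints 0.27 to 0.73 and is 0.30 to 0.70 at a true 90%.

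**Step 5: smaller sets and sensitivity.** SAP Section 4 and its Table 6 also split Cohort 1 RAL-naïve by first dose. Protocol Section 1.29 puts 6 infants at 3 mg/kg, which leaves 10 − 6 = 4 at 2 mg/kg; 0/4 has an upper limit of 0.53. If one Cohort 1 RAL-exposed infant was not dosed, 0/5 gives 0.45.

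**The case against.** The best defence is that Table 14 describes cohorts, not exposure groups. Its rows are labelled by cohort, 12 and 20 are the declared cohort minimums, and Section 8.53 works with the same 12, 8 and 20. Illustrating precision at planned minimums is ordinary practice and is conservative for totals. Cohort totals are planned too, conditionally in the protocol and always in the SAP. The results will carry each subgroup's own interval, so nobody reading the final report will be misled.

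Much of this stands. A reader might infer that Table 14 flatters Cohort 1 as a whole; the documents do not support that. The 16 pooled infants give 0.17, better than the printed 0.26, and the 10 RAL-naïve infants match the printed figure. A reader might also put the whole Cohort 2 RAL-naïve gap down to group size, but about half of it comes from the confidence level. Nor should 8 and 34 be read as sizes actually analysed: the Schema's 8 is itself a PK-evaluable minimum, and the number dosed may be larger.

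The defence does not remove the mismatch. Section 8.7.1 names the four groups as the units of summary and makes the pooled figure conditional, so a table of cohort minimums does not show what those estimates can deliver. Even for pooled cohorts, 12 and 20 are not the sizes. Cohort 2 RAL-exposed does have a row at its minimum size, but labelled as the interim analysis; a reader who took the n=20 final row for that group would see 0.17 where 0.31 applies at n=8.

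**Conclusion.** The point holds as a minor mismatch between the precision table and the analysis set. Measured against what is printed, Table 14 is too favourable for Cohort 1 RAL-exposed (0.26 where 0.39 applies, 13 points) and too pessimistic for Cohort 2 RAL-naïve (0.17 where 0.11 applies, 6 points, half of it from the level). Both pooled cohorts do better than printed.

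This rests on all enrolled infants having been dosed. For Cohort 1, Section 1.29 supports that by reporting that all infants received the second dose. For Cohort 2 RAL-naïve, 26 is an enrolment count.

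A reader might infer that the safety guidelines are affected. They are not: the analysis is descriptive, and the pass and suspension rules in Section 8.52 do not use Table 14. The wrong confidence level is the more definite fault in the table, but correcting it alone would leave the sizes wrong and would widen the visible Cohort 1 RAL-exposed gap to 17 points.

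**What to change.** Recompute Table 14 at the stated 90% level and, in the same run:
- replace the 12 and 20 rows with safety-evaluable numbers per exposure group and pooled cohort: 6, 10 and 16 for Cohort 1; 26, 8 and 34 for Cohort 2;
- mark 8 and 34 as minimums, and label the 8 row as the Cohort 2 RAL-exposed final analysis as well as the interim sample;
- state in one sentence that the rows count safety-evaluable infants and assume that all enrolled infants were dosed;
- if the SAP's dose subgroups are kept, add n=4.

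The cost is one table and one sentence. Among the four groups, only Cohort 1 RAL-exposed then shows less favourable precision than the row now printed for it. No sample size, endpoint or decision rule changes.
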